	
dose level for subsequent cycles. Further dose reductions must be discussed with the study PI and sponsor. If patient is already at the lowest dose of study drug, please discuss with the study PI and Daiichi regarding study continuation or discontinuation decision.
 
• Transfusion of red blood cells as per treating physician discretion is allowed.• For any dose delays greater than 28 days, decision regarding study continuation or discontinuation should be discussed with the study PI and Daiichi.
--	--

*Please see Section 11.7 for more details on the use of G-CSF in the setting of severe neutropenia or neutropenic fever.

Dose Modifications with Concomitant Strong CYP3A Inhibitors and/or P-gp Inhibitors

When drugs with strong CYP3A inhibitory effect and/or P-gp inhibitory effect are coadministered, the dose of the study drug should be reduced according to table 5.1. The dose of the study drug should be returned to the previous dose level that the subject was given after 3 days from the last dose of the concomitant strong CYP3A inhibitors and/or P-gp inhibitors.

Table 5.1 Dose Delays and Modifications for Concomitant Strong CYP3A Inhibitors and/or P-gp Inhibitors

Inhibitor	DS-3201b Dose	
	200 mg Once Daily	150 or 100 mg Once Daily*
Strong CYP3A inhibitors	Reduce the dose of the study drug to 100 mg once daily	Reduce the dose off the study drug to 50mg once daily
P-gp inhibitors	Reduce the dose of the study drug to 100 mg once daily	Reduce the dose off the study drug to 50mg once daily
Drugs having a strong CYP3A inhibitory effect and a P-gp inhibitory effect	Reduce the dose off the study drug to 50mg once daily	Interrupt the study drug

CYP3A = cytochrome P4503A; P-gp = P-glycoprotein

*When the dose of study drug DS-3201b is 150mg or 100mg once daily, the investigator should consult Daiichi's medical monitor before further reduction of the dose due to concomitant use of strong CYP3A or/and P-gp inhibitors.

Table 6.0 Dose Delays and Modifications for All Other Non-Hematologic TEAEs

Toxicity Grade	Modification instructions

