Other Laboratory Adverse Events (DS-3201b drug related Grade 3 that require treatment)	
Interrupt administration of study drug DS-3201b up to 28 days.Resume the study drug DS-3201b at the dose before interruption once resolved to \leqGrade 1 or baseline value within 28 days after interrupting study drug.If a second dose interruption is required for the same drug-related adverse event, then decrease study drug DS-3201b dose by 1 dose level for subsequent cycles. Further dose reductions must be discussed with the study PI and sponsor. If patient is already at the lowest dose of study drug, please discuss with the study PI and Daiichi regarding study continuation or discontinuation decision. Exceptions:
○ Transient laboratory abnormalities (DS-3201b-related) that do not involve associated clinical signs or symptoms and that resolve within 72 hours after onset

	
For any dose delays greater than 28 days, decision regarding study continuation or discontinuation should be discussed with the study PI and sponsor.
Other Laboratory Adverse Events (DS-3201b drug related Grade 4)	
Interrupt administration of study drug DS-3201b up to 28 days.Resume the study drug DS-3201b at a reduced dose (by 1 dose level) for the subsequent cycles once resolved to \leqGrade 1 or baseline conditionIf a second dose interruption is required for the same drug-related adverse event, discontinue subject from studySubjects who experience a \geqGrade 3 laboratory AE who are, in the opinion of the investigator, benefiting from treatment may be allowed to continue study drug.
Other Non-Laboratory and Laboratory Adverse Events (regardless of causality, any AE, lab abnormality or intercurrent illness that presents a substantial clinical risk to the subject with continued dosing per the investigator's opinion)	
Interrupt administration of study drug DS-3201b until there is no longer a substantial clinical risk to the subject with continued dosing of the study drug DS-3201b per the investigator's opinionResume the study drug DS-3201b at the same dose level
AEs Grade 1-2	
Proceed with full-dose treatment of all agents.

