If DS-3201b needs to be held for any TEAEs as above, irinotecan should be held as well. When both study drugs are held for any particular visit due to TEAEs, counting of dose cycles will hold until their TEAEs have resolved or improved enough to meet protocol guidelines to restart treatment with both study drugs. If both drugs are held longer than 1 cycle (21 days), the treating physician must discuss eligibility for the patient to continue treatment on study with the study PI.

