11.6 Dose Delays and Modifications for Irinotecan

During Cycle 1 of Phase I dose-escalation, which includes the initial 7 days of safety run-in from Day -7 to Day 0, dose delays and dose modifications of irinotecan will not be used unless a DLT has been declared for purposes of determining the MTD. The outlined dose delays and modifications for both DS-3201b and irinotecan will be used in all patients in Phase I Cycle 1 if DLT has been declared, in all subsequent cycles of Phase I, and in all cycles of Phase II of this study. If toxicities are encountered, dosing adjustments and delays of DS-3201b and/or irinotecan will be made based on determination of the likely causative agent as outlined above

in Sections 11.2 and 11.3. Determination of the likely causative agent will be dependent on the treating physician if they feel that the toxicity is at least possibly related to either or both of the study drugs.

Usual clinical practice for dose delay and modification of irinotecan will be used, and dose adjustments will occur independent of DS-3201b dosing adjustments.

Patients should return to pre-treatment bowel function without requiring antidiarrhea medications for at least 24 hours before the next chemotherapy administration. A new cycle of therapy should not begin until the granulocyte count has recovered to $\geq 1500/\text{mm}^3$, and the platelet count has recovered to $\geq 100,000/\text{mm}^3$, and treatment-related diarrhea is fully resolved. Treatment should be delayed 1 to 2 weeks to allow for recovery from treatment-related toxicities. If the patient has not recovered after a 2-week delay, consideration should be given to discontinuing therapy.

If both study drugs are held for any particular visit due to TEAEs, then the patient would restart that same visit when their TEAEs have resolved or improved enough to meet protocol guidelines to restart treatment with either one or both study drugs.

If irinotecan needs to be held for any TEAEs as above, patients will have the option to continue DS-3201b as long as the TEAE is not also attributed to DS-3201b. However, counting of dose cycles will hold until their TEAEs have resolved or improved enough to meet protocol guidelines to restart treatment with irinotecan, regardless of whether patient continues DS-3201b. If both drugs are held longer than 1 cycle (21 days), the treating physician must discuss eligibility for the patient to continue treatment on study with the study PI.

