When administered in combination with other agents, or as a single agent, a reduction in the starting dose by at least one level of irinotecan should be considered for patients known to be homozygous for the UGT1A1*28 allele.

If dose level reduction below Level -2 is needed to manage toxicity due to irinotecan, then study treatment with both DS-3201b and irinotecan will be permanently discontinued.

Table 7.0 Dose Levels for Irinotecan^a

Starting Dose	125 mg/m ²
Dose Level -1	100 mg/m ²
Dose Level -2	75 mg/m ²

^a As per standardized prescribing information in the United States.

Table 8.0 Recommended Dose Modifications for Irinotecan in Combination-Regimens

CTCAE v5.0 Toxicity Grade	During a Cycle of Therapy	At the Start of Subsequent Cycles of Therapy ^a
No toxicity	Maintain dose level	Maintain dose level

Neutropenia*		
1 (1500 to 1999/mm ³)	Maintain dose level	Maintain dose level
2 (1000 to 1499/mm ³)	↓ 1 dose level	Maintain dose level
3 (500 to 999/mm ³)	Omit dose until resolved to ≤ grade 2, then ↓ 1 dose level	↓ 1 dose level
4 (<500/mm ³)	Omit dose until resolved to ≤ grade 2, then ↓ 2 dose levels	↓ 2 dose levels
Neutropenic fever	Omit dose until resolved, then ↓ 2 dose levels	
Other hematologic toxicities	Dose modifications for leukopenia or thrombocytopenia during a cycle of therapy and at the start of subsequent cycles of therapy are also based on NCI toxicity criteria and are the same as recommended for neutropenia above.	
Diarrhea^c		
1 (≤4 stools/day > pretx ^b)	Delay dose until resolved to baseline, then give same dose	Maintain dose level
2 (4-6 stools/day > pretx)	Omit dose until resolved to baseline, then ↓ 1 dose level	Maintain dose level
3 (≥7 stools/day > pretx; hospitalization indicated)	Omit dose until resolved to baseline, then ↓ 1 dose level	↓ 1 dose level
4 (life-threatening; urgent intervention indicated)	Omit dose until resolved to baseline, then ↓ 2 dose levels	↓ 2 dose levels
Other non-hematologic toxicities^d		
1	Maintain dose level	Maintain dose level
2	Omit dose until resolved to ≤ grade 1, then ↓ 1 dose level	Maintain dose level
3	Omit dose until resolved to ≤ grade 2, then ↓ 1 dose level	↓ 1 dose level
4	Omit dose until resolved to ≤ grade 2, then ↓ 2 dose levels	↓ 2 dose levels

*Please see Section 11.7 for more details on the use of G-CSF in the setting of severe neutropenia or neutropenic fever.

^a Relative to the starting dose in the previous cycle.

^b Pretreatment.

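### The Grade 1-2 row of Table 6.0 orders full dose of both drugs, but Table 8.0 and Section 11.6 require irinotecan to be delayed, or omitted and then reduced, for some of the same events

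*Combined protocol and SAP*

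**What the plan says.** Table 6.0 stands in Section 11.5.4, the DS-3201b dose-modification section, under the title "Dose Delays and Modifications for All Other Non-Hematologic TEAEs". Its final row, for Grade 1-2 adverse events, reads "Proceed with full-dose treatment of all agents". Where the earlier rows give dosing instructions, they name DS-3201b. Directly below the table, the same section also directs the other drug: "If DS-3201b needs to be held for any TEAEs as above, irinotecan should be held as well".

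Section 11.6 and its Table 8.0 set the irinotecan rules. During a cycle:

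- Grade 1 diarrhea: "Delay dose until resolved to baseline, then give same dose".
- Grade 2 diarrhea: "Omit dose until resolved to baseline", followed by a reduction of one dose level.
- Other Grade 2 non-hematologic toxicity: omit until Grade 1 or lower, then reduce one level. A footnote exempts alopecia, anorexia and asthenia.

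The text of Section 11.6 adds a recovery condition: "Patients should return to pre-treatment bowel function without requiring antidiarrhea medications for at least 24 hours before the next chemotherapy administration". It also bars a new cycle until treatment-related diarrhea has fully resolved. Sections 11.5.4 and 11.6 both apply the modification rules for both drugs to all Phase II cycles, to Phase I cycles after the first, and to Phase I Cycle 1 once a DLT has been declared.

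**The concern.** The two tables cover the same events in the same cycles and give different instructions for irinotecan. A site that follows the Table 6.0 row as written gives full-dose irinotecan on schedule through active Grade 1 or 2 diarrhea. A site that follows Table 8.0 holds the dose and, at Grade 2, lowers it.

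Sites will meet this case. Sections 11.3.2 and 11.4.3 list diarrhea as common for DS-3201b and for irinotecan, and Section 3.6 reports it in 22 of 81 subjects (27.2%) in the DS-3201b lymphoma study. Section 11.7 warns that late irinotecan diarrhea can threaten life, so the literal reading of Table 6.0 is the less safe one. Phase II runs at two centers, which could settle the conflict differently. What is at stake is patient safety and uniform dosing. The primary endpoint and the design are not at issue.

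**Working it through.** The plan gives no figure to reproduce here. The check compares the two tables cell by cell and then converts one conflicting cell into dose.

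**Comparison for irinotecan**

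| Event | Table 6.0, Grade 1-2 row | Table 8.0 / Section 11.6 | Conflict |
|---|---|---|---|
| Diarrhea Grade 1, during a cycle | Full dose, no delay | Wait for baseline, same dose | Timing only |
| Diarrhea Grade 2, during a cycle | Full dose, no delay | Omit, then one level lower | Timing and dose |
| Other non-hematologic Grade 2, during a cycle (except alopecia, anorexia, asthenia) | Full dose, no delay | Omit, then one level lower | Timing and dose |
| Other non-hematologic Grade 1, during a cycle | Full dose | Dose level kept | None |
| Grade 1-2 at the start of a later cycle | Full dose | Dose level kept, but treatment-related diarrhea must first resolve | None on dose level; timing for diarrhea |

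**Size for Grade 2 diarrhea at Cycle 1 Day 8**

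Inputs: irinotecan 125 mg/m² on Days 1 and 8 (Section 9.1); dose level -1 is 100 mg/m² (Table 7.0).

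- Planned Cycle 1 dose: 2 × 125 = 250 mg/m².
- Table 6.0: (125 + 125)/250 = 250/250 = 100%.
- Table 8.0, Day 8 dose given late at level -1: (125 + 100)/250 = 225/250 = 90%.
- Table 8.0, Day 8 dose never given: 125/250 = 50%.

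The 90% case is what Table 8.0 produces when the patient recovers, because Section 11.6 says that "counting of dose cycles will hold until their TEAEs have resolved". The 50% case is the lower bound.

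**Grade 1 diarrhea at the same visit:** (125 + 125)/250 = 100% under both tables, later under Table 8.0.

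**Possible link to the DLT definition**

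The DLT section counts a patient as having a DLT if non-disease-related Grade 2 or higher events prevent completion of at least 75% of the prescribed doses in the evaluation period. Applied to irinotecan by amount, the threshold is 0.75 × 250 = 187.5 mg/m². The 225 mg/m² case is above it and the 125 mg/m² case is below it. Two limits apply:

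- The section glosses the clause as 21 days. That equals 0.75 × 28, the run-in plus Cycle 1, so it describes daily dosing. Carrying it over to two infusions is an interpretation.
- It would matter only for the Phase II toxicity count, because dose modifications are not used in Phase I Cycle 1 unless a DLT has already been declared.

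**The case against.** The best reply is that the surrounding text already points to Table 8.0. Table 6.0 belongs to the DS-3201b section. Section 11.6 says that irinotecan adjustments are made independently of those for DS-3201b and that adjustments follow the likely causative agent. It also foresees irinotecan being held on its own: "patients will have the option to continue DS-3201b as long as the TEAE is not also attributed to DS-3201b". A dedicated, toxicity-specific irinotecan table would normally override one general row in another drug's section. The sentence tying irinotecan to DS-3201b holds works only toward stopping, so it does not support forcing a full dose. Investigators may also interrupt treatment for any event that poses substantial clinical risk, and Table 8.0 is itself headed as recommended modifications.

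Much of this stands. The likely intent is that Table 8.0 governs, and a careful site would probably read it that way. The 50% figure also reflects failure to recover under Table 8.0, so 100% versus 90% is the fairer measure of the conflict, and the DLT link deserves little weight.

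The reply does not remove the contradiction. No sentence ranks the two tables. The row departs from its neighbors by naming all agents, and the section around it does direct irinotecan elsewhere. Both rule sets are in force together, and a site cannot comply with the row and with Section 11.6's bowel-recovery condition at the same visit.

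**Conclusion.** The concern holds and is minor. The Grade 1-2 row of Table 6.0 conflicts with three during-cycle cells of Table 8.0 and with Section 11.6's bowel-recovery conditions.

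For Grade 2 diarrhea at Cycle 1 Day 8, the irinotecan difference is 100% versus 90% of the planned cycle dose if the patient recovers and is treated late, and 100% versus 50% at worst. For Grade 1 diarrhea it is timing alone. These figures assume that Day 1 was given at 125 mg/m² and that this was the only event affecting the dose.

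The response threshold, sample size and stopping boundaries do not change. Only the 50% case could reach the Phase II toxicity count, and only if the 75% clause is read as covering infusions.

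**What to change.** Replace the instruction in the Grade 1-2 row of Table 6.0 with: *Proceed with full-dose DS-3201b; for irinotecan follow Section 11.6 and Table 8.0.* Keep Section 11.6's existing limit, under which DS-3201b may continue while irinotecan is held only if the event is not also attributed to DS-3201b. A short cross-reference to that limit in the row would stop the new wording from being read as overriding it.

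The cost is one table row in the next amendment. Design, sample size and data collection stay as they are.

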11.6 Dose Delays and Modifications for Irinotecan

During Cycle 1 of Phase I dose-escalation, which includes the initial 7 days of safety run-in from Day -7 to Day 0, dose delays and dose modifications of irinotecan will not be used unless a DLT has been declared for purposes of determining the MTD. The outlined dose delays and modifications for both DS-3201b and irinotecan will be used in all patients in Phase I Cycle 1 if DLT has been declared, in all subsequent cycles of Phase I, and in all cycles of Phase II of this study. If toxicities are encountered, dosing adjustments and delays of DS-3201b and/or irinotecan will be made based on determination of the likely causative agent as outlined above

in Sections 11.2 and 11.3. Determination of the likely causative agent will be dependent on the treating physician if they feel that the toxicity is at least possibly related to either or both of the study drugs.

Usual clinical practice for dose delay and modification of irinotecan will be used, and dose adjustments will occur independent of DS-3201b dosing adjustments.

Patients should return to pre-treatment bowel function without requiring antidiarrhea medications for at least 24 hours before the next chemotherapy administration. A new cycle of therapy should not begin until the granulocyte count has recovered to $\geq 1500/\text{mm}^3$, and the platelet count has recovered to $\geq 100,000/\text{mm}^3$, and treatment-related diarrhea is fully resolved. Treatment should be delayed 1 to 2 weeks to allow for recovery from treatment-related toxicities. If the patient has not recovered after a 2-week delay, consideration should be given to discontinuing therapy.

If both study drugs are held for any particular visit due to TEAEs, then the patient would restart that same visit when their TEAEs have resolved or improved enough to meet protocol guidelines to restart treatment with either one or both study drugs.

If irinotecan needs to be held for any TEAEs as above, patients will have the option to continue DS-3201b as long as the TEAE is not also attributed to DS-3201b. However, counting of dose cycles will hold until their TEAEs have resolved or improved enough to meet protocol guidelines to restart treatment with irinotecan, regardless of whether patient continues DS-3201b. If both drugs are held longer than 1 cycle (21 days), the treating physician must discuss eligibility for the patient to continue treatment on study with the study PI.

When administered in combination with other agents, or as a single agent, a reduction in the starting dose by at least one level of irinotecan should be considered for patients known to be homozygous for the UGT1A1*28 allele.

If dose level reduction below Level -2 is needed to manage toxicity due to irinotecan, then study treatment with both DS-3201b and irinotecan will be permanently discontinued.

Table 7.0 Dose Levels for Irinotecan^a

Starting Dose	125 mg/m ²
Dose Level -1	100 mg/m ²
Dose Level -2	75 mg/m ²

^a As per standardized prescribing information in the United States.

Table 8.0 Recommended Dose Modifications for Irinotecan in Combination-Regimens

CTCAE v5.0 Toxicity Grade	During a Cycle of Therapy	At the Start of Subsequent Cycles of Therapy ^a
No toxicity	Maintain dose level	Maintain dose level

Neutropenia*		
1 (1500 to 1999/mm ³)	Maintain dose level	Maintain dose level
2 (1000 to 1499/mm ³)	↓ 1 dose level	Maintain dose level
3 (500 to 999/mm ³)	Omit dose until resolved to ≤ grade 2, then ↓ 1 dose level	↓ 1 dose level
4 (<500/mm ³)	Omit dose until resolved to ≤ grade 2, then ↓ 2 dose levels	↓ 2 dose levels
Neutropenic fever	Omit dose until resolved, then ↓ 2 dose levels	
Other hematologic toxicities	Dose modifications for leukopenia or thrombocytopenia during a cycle of therapy and at the start of subsequent cycles of therapy are also based on NCI toxicity criteria and are the same as recommended for neutropenia above.	
Diarrhea^c		
1 (≤4 stools/day > pretx ^b)	Delay dose until resolved to baseline, then give same dose	Maintain dose level
2 (4-6 stools/day > pretx)	Omit dose until resolved to baseline, then ↓ 1 dose level	Maintain dose level
3 (≥7 stools/day > pretx; hospitalization indicated)	Omit dose until resolved to baseline, then ↓ 1 dose level	↓ 1 dose level
4 (life-threatening; urgent intervention indicated)	Omit dose until resolved to baseline, then ↓ 2 dose levels	↓ 2 dose levels
Other non-hematologic toxicities^d		
1	Maintain dose level	Maintain dose level
2	Omit dose until resolved to ≤ grade 1, then ↓ 1 dose level	Maintain dose level
3	Omit dose until resolved to ≤ grade 2, then ↓ 1 dose level	↓ 1 dose level
4	Omit dose until resolved to ≤ grade 2, then ↓ 2 dose levels	↓ 2 dose levels

*Please see Section 11.7 for more details on the use of G-CSF in the setting of severe neutropenia or neutropenic fever.

^a Relative to the starting dose in the previous cycle.

^b Pretreatment.

^c Loperamide as needed can be administered to the patient for relief of symptoms once the toxicity grade has been determined. The dosing and frequency of loperamide can vary per patient and will be determined by the treating physician.

^d Excludes alopecia, anorexia, asthenia.

11.7 Management Guidelines for Irinotecan-Induced Diarrhea

Early diarrhea (occurring during or shortly after infusion of irinotecan) is usually transient and infrequently severe. It may be accompanied by cholinergic symptoms of rhinitis, increased salivation, miosis, lacrimation, diaphoresis, flushing, and intestinal hyperperistalsis that can cause abdominal cramping. Bradycardia may also occur. Early diarrhea and other cholinergic

symptoms may be prevented or treated. Prophylactic or therapeutic administration of 0.25 mg to 1 mg of intravenous or subcutaneous atropine (unless clinically contraindicated) can be used if this occurs.

Late diarrhea (generally occurring more than 24 hours after administration of irinotecan) can be life threatening since it may be prolonged and may lead to dehydration, electrolyte imbalance, or sepsis. In the clinical studies, the median time to the onset of late diarrhea was 5 days with 3-week dosing and 11 days with weekly dosing. Late diarrhea can be complicated by colitis, ulceration, bleeding, ileus, obstruction, and infection. Cases of megacolon and intestinal perforation have been reported. Patients should have loperamide readily available to begin treatment for late diarrhea. Patients will be instructed to begin loperamide at the first episode of poorly formed or loose stools or the earliest onset of bowel movements more frequent than normal. One dosage regimen for loperamide is 4 mg at the first onset of late diarrhea and then 2 mg every 2 hours until the patient is diarrhea-free for at least 12 hours. Loperamide is not recommended to be used for more than 48 consecutive hours at these doses because of the risk of paralytic ileus. During the night, the patient may take 4 mg of loperamide every 4 hours.

11.8 7 Use of Granulocyte Colony-Stimulating Factors (G-CSF)

According to guidelines from the American Society of Clinical Oncology (ASCO) and the European Society for Medical Oncology (ESMO), primary prophylaxis with granulocyte colony-stimulating factors (G-CSF) is not allowed. However, secondary prophylaxis with G-CSF for neutropenia as per usual standard clinical practice is allowed, even during the initial DLT evaluation period (safety run-in + Cycle 1).^{29,30}

11.9 8 Definitions of Dose-Limiting Toxicity (DLT)

Although all toxicities will be closely monitored and graded throughout the entire study treatment, only toxicities occurring during Cycle 1 of treatment (initial 7-day safety run-in plus the first 21 days) that meet the definition of DLT will influence the determination of MTD. Any toxicity during Cycle 1 of treatment that meets the definition of DLT as described below, whether it is attributed to either DS-3201b or irinotecan or both, will affect the determination of MTD during the Phase I portion of the study.

Dose-limiting toxicity (DLT) is defined as a clinically significant non-hematologic treatment-emergent adverse event (TEAE) or abnormal clinical laboratory value that is clearly **NOT** related to disease progression, intercurrent illness, and occurring during the DLT evaluation period (safety run-in + Cycle 1) on study that meets any of the following criteria:

Hematologic dose-limiting toxicity is defined as any:

- All Grade ≥ 3 adverse event that are at least possibly related to study treatment with the following exceptions:
 - Grade 4 neutropenia lasting less than 7 consecutive days.
 - Grade 3 neutropenia without fever and/or infection where fever is an oral temperature $\geq 38.5^{\circ}\text{C}$.

- Grade 4 thrombocytopenia (platelet count<25,000/mm³) lasting less than 7 consecutive days. *However, a platelet count <10,000/mm³ at any time for any duration will count as a DLT.*
- Grade 3 thrombocytopenia without bleeding.

Non-Hematologic dose-limiting toxicity is defined as any:

- All Grade ≥3 adverse events that are at least possibly related to study treatment with the following exceptions:
 - Grade 3 aspartate aminotransferase AST (SGOT) or alanine aminotransferase (ALT) (SGPT) or bilirubin for ≤ 7 days.
 - Grade 3 or 4 nausea, vomiting, and diarrhea that do not require hospitalization or total parenteral nutrition (TPN) support and can be managed with supportive care to ≤ Grade 2 within 48 hours.
 - Electrolyte abnormalities that are corrected to ≤ Grade 2 within 24 hours.
 - Alopecia and study drug-related fever (without Grade 3 neutropenia) will not constitute DLT.
 - Any Grade 5 adverse event proven to be clearly and incontrovertibly related to disease progression or intercurrent illness and not possibly related to study drug DS-3201b.

If the treating physician determines that a TEAE occurring during the DLT evaluation period which met the definition for DLT is due to underlying disease progression or intercurrent illness and NOT due to study drug effect from either DS-3201b and irinotecan, a final determination regarding DLT determination will be discussed with the study PI.

Patients who are unable to complete at least 75% of the prescribed dose (i.e., 21 days) of DS-3201b and irinotecan during the DLT evaluation period (safety run-in + Cycle 1) due to non-disease-related ≥ Grade 2 adverse events will be considered to have a DLT. These same DLT definitions detailed above in this section will also apply for the entire duration of the Phase II portion of the study as it pertains to the toxicity stopping rule (please see Section 14.0 for more details).

